2.2 Dose-Response Model Primary

We label the mean change from baseline to 52-weeks for dose group d as θ_d . We construct a dose-response model for the mean change from baseline for each treatment arm. The arms are modeled with a two-dimensional first-order normal dynamic linear model (NDLM). This model is a Gaussian random walk model. The structure is

$$\begin{aligned} [\theta_0] &\sim N(0, 0.5^2) \\ [\theta_1] &\sim N(0, 0.5^2) \end{aligned}$$

□

and the NDLM structure for the bi-monthly doses:

$$[\theta_2] \sim N(\theta_1, \tau^2)$$

□

$$[\theta_3] \sim N(\theta_2, \tau^2)$$

The monthly doses are “connected” to the dose-response model through the respective bi-monthly doses. The connection through the NDLM first order structure results in the following priors

$$[\theta_4] \sim N(\theta_2, \tau^2)$$

and

$$[\theta_5] \sim N\left(\frac{\theta_3 + \theta_4}{2}, \frac{\tau^2}{2}\right).$$

The drift parameter (variance component), τ^2 is modeled with the following prior distributions:

$$[\tau^2] \sim IG(0.25, 0.0025)$$

where $IG(a, b)$ is the inverse gamma distribution with shape parameter a and scale parameter b . This prior has the equivalent weight of 0.5 observations worth of weight that the value of τ is 0.1.

The prior distribution on the initial dose is selected to be a vague prior. An effect size of 0.03 is considered clinically significant and the standard error of the clinical scale is 0.15. Therefore these priors are quite weak and allow the data to shape the dose-response model. The prior for the “drift parameter” is selected to have minor weight that there will be similarity across the doses, and hence a minor amount of borrowing. With 5 doses the amount of borrowing is determined largely by the similarity in outcomes across doses.

The distribution of the variance of the primary endpoint, σ^2 , is modeled with the following prior:

$$[\sigma^2] \sim IG(2.5, 0.056).$$

The prior is equivalent to a prior weight of 5 observations worth of information that the value of σ is 0.15. The value of 0.15 is based on initial modeling by Eisai. This prior allows the historical data estimate of 0.15 to have some role in the early part of the trial. When 300 subjects have been enrolled this prior will have a very minor role (5/305 weight is less than 2%).

2.3 Longitudinal Model

At each interim analysis there will be subjects who have complete or incomplete information. Some subjects will have complete information meaning they have a 52-week value observed, $Y_{i,52}$. These subjects may also have their earlier values observed, $Y_{i,6}$, $Y_{i,12}$, $Y_{i,26}$, and $Y_{i,39}$. There will be subjects with earlier observations, but no 52-week observation. There will be subjects with no observations.

We utilize the information from subjects with incomplete information to the extent that the earlier values are correlated to the final 52-week value. A Bayesian model is built to learn from the accruing information on the association between the early values and the final endpoint at 52 weeks. Different sets of parameters (instances) are used for each arm in the trial, but the models correlating early to late outcomes are the same.

A linear regression model is created for the correlation between the 6-, 12-, 26-, and 39-week values and the 52-week value (we suppress the subject index i and refer to the change from baseline at weeks 6, 12, 26, 39, and 52 as Y_6 , Y_{12} , Y_{26} , Y_{39} , and Z_{52}). A common model is used for each active dose and a separate model for the control. Each of the model instances is identical, with the following structure for early time period j :

$$\begin{aligned} [Z_{52} | Y_j] &\sim N(\alpha_j + \beta_j Y_j, \lambda_j^2) \\ [\alpha_j] &\sim N(0, 0.05^2) \\ [\beta_j] &\sim N(0.80, 0.25^2) \\ [\lambda_j^2] &\sim IG(2.5, 0.025). \end{aligned}$$

The prior distribution for the standard deviation about the linear regression, λ , has a prior mean estimate of 0.10 with a weight of 5 observations. The joint posterior distribution of α_j , β_j , and λ_j , for $j=6, 12, 26$, and 39 , are updated at each interim analysis (as described in [Section 4.0](#)) with the observed values of Y_{52} .

These prior distributions were selected from historical data provided by Eisai. The data were discounted to allow the new study to shape the posteriors, but these priors provide empirically based starting values.

At each interim analysis (as described in [Section 4.0](#)), this model is used, with Bayesian imputation within Markov chain Monte Carlo, to update the dose-response model at each interim analysis. The Markov chain Monte Carlo steps are as follows:

- 1). Simulate longitudinal model parameters from the updated joint posterior distribution
- 2). For patients that do not yet have a 52 week observation, impute the 52 week observation based on their most recent observation (6, 12, 26, or 39 weeks)
- 3). Simulate dose-response model parameters for each arm based on the “complete” (observed and imputed) 52-week data.
- 4). Repeat

3.0 POSTERIOR QUANTITIES

3.1 Definition of Doses

We characterize the dose-response curve by defining the maximum effective dose (d_{Max}) and the effective dose 90 (d_{ED90}). The maximum effective dose (d_{Max}) is the dose with the greatest

treatment effect (greatest difference from control in mean change from baseline to 52 weeks). The d_{ED90} is the simplest dose that achieves at least 90% of the treatment effect achieved by d_{Max} . The simplest dose level is the smallest dose level with the lowest frequency of administration. The dose levels ordered by frequency of administration and amount are 5QM, 10QM, 3BM, 5BM, and 10BM. The doses identified as the d_{Max} and the d_{ED90} may be different doses or the same dose. For example, if only one dose is effective, it would be both the d_{Max} and d_{ED90} .

We estimate the probability each dose is d_{Max} , $\Pr(d = d_{Max})$, and the probability each dose is the d_{ED90} , $\Pr(d = d_{ED90})$. Based on the posterior distributions of the parameters in the dose response model, we sample 10,000 dose-response curves. We identify the d_{Max} and the d_{ED90} for each of these curves. The proportion of simulated dose-response curves where $d = d_{Max}$ is the $\Pr(d = d_{Max})$ for a given dose d . Similarly, the proportion of simulated dose-response curves where $d = d_{ED90}$ is the $\Pr(d = d_{ED90})$ for a given dose d .

3.2 Probability Superior to Control

For each dose we calculate the probability of being superior to control by comparing the posterior distribution of the mean change from baseline to 52-weeks between the active dose and the control.

We determine the probability of being superior to control by randomly drawing 10,000 treatment effects from the posterior distribution of θ_d for the active dose, and a matching 10,000 samples from the posterior distribution of θ_0 (treatment effects for the control). Thus, we have 10,000 pairs of active dose and control treatment effects. The proportion of pairs where the treatment effect for the active dose is greater than for control is the probability of being superior to control, $\Pr(\theta_d > \theta_0)$.

3.3 Probability Superior to Control by Clinically Significant Difference

Similar to above in Section 3.2, we calculate the probability of being superior to control by at least the clinically significant difference (CSD) of 0.03 by comparing the posterior distribution of the mean change from baseline to 52 weeks between the active dose and the control.

We determine the probability of being superior to control by at the least the CSD by sampling 10,000 treatment effects from the posterior distribution of θ_d for the active dose, and a matching 10,000 samples from the posterior distribution of θ_0 (treatment effect for the control). Thus, we have 10,000 pairs of active dose and control treatment effects. The proportion of pairs where the treatment effect for the active dose is greater than for control by at least 0.03 is the probability of being superior to control by at least the CSD, $\Pr(\theta_d > \theta_0 + 0.03)$.

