5.4 EFFICACY ANALYSES

5.4.1 Primary Efficacy Analyses

The primary analysis will be based on subjects from the Full Analysis Set with the prespecified censoring rules applied. The primary endpoint is the change from baseline to 12 months in the derived ADCOMS. The derived ADCOMS is a weighted linear combination of 12 items from the three existing clinical scales, the ADAS-cog, the MMSE, and the CDR. These 12 items consist of the predictive variables A4, A7, A8, A11, M1, M7, C1, C2, C3, C4, C5 and C6, which have been selected from the clinical scales, the ADAS-cog, the MMSE, and the CDR. The names of these item and the corresponding scale names are described in [Table 2](#).

Table 2: Predictive Variables for the Derived ADCOMS

Scale	Item ID	Item Name	PLS weight
ADAS-cog	A4	Delayed Word Recall	0.00847483
	A7	Orientation	0.017088
	A8	Word Recognition	0.003732761
	A11	Word Finding	0.016211
MMSE	M1	Orientation Time	0.041567
	M7	Drawing	0.038238
CDR	C1	Personal Care	0.054321
	C2	Community Affairs	0.1091
	C3	Home and Hobbies	0.089039
	C4	Judgment and Problem Solving	0.069493
	C5	Memory	0.058724
	C6	Orientation	0.078152

ADAS-cog = Alzheimer's Disease Assessment Scale, cognitive subscale, CDR = Clinical Dementia Rating, ID = identification, MMSE = Mini Mental State Examination, PLS = Partial Least Squares.

The derived composite score will be calculated from these predictive variables according to the formula:

$$\text{Derived composite Score} = A4 * 0.00847483 + A7 * 0.017088 + A8 * 0.003732761 + A11 * 0.016211 + (5-M1) * 0.041567 + (1-M7) * 0.038238 + C1 * 0.054321 + C2 * 0.1091 + C3 * 0.089039 + C4 * 0.069493 + C5 * 0.058724 + C6 * 0.078152.$$

The maximum derived composite score is achieved when each item is assigned the maximum score. This maximum composite score is 1.97. The range of this new composite score is therefore between 0 and 1.97.

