5.4.2 Adaptive Trial Definitions

Clinically Significant Difference (CSD): The CSD used in the adaptive model relative to the change from baseline over time for placebo in the derived ADCOMS. The CSD for this study represents an approximate 25% reduction compared to placebo in the progression of AD as measured by the derived ADCOMS.

Maximum Effective Dose (d_{Max}): The dose that achieves the greatest treatment effect.

ED₉₀: The ‘simplest’ dose regimen that achieves at least 90% of the d_{Max} treatment effect. The term ‘simplest’ reflects the preference for dosing frequency and amount when considering the treatment arms for the study and while taking efficacy into account (monthly administration is preferred over bi-weekly administration and lower doses are preferred over higher doses, with priority placed on frequency of administration). Thus, the rank order of prioritized doses (beginning with the simplest) is: 5 mg/kg Q4wk, 10 mg/kg Q4wk, 2.5 mg/kg Q2wk, 5 mg/kg Q2wk, and 10 mg/kg Q2wk.

Early Success: The study meets early success criteria if the probability that the ED₉₀ at 12 months of treatment is better than the placebo by the CSD is at least 0.95. Early success is achieved before all subjects complete 12 months of treatment and can only be determined once ≥ 350 subjects are randomized. If early success is declared prior to full randomization, the randomization of new subjects will stop. Subjects already randomized into the study will receive 18 months of treatment.

Futility: The study meets statistical futility criteria if the probability that the ED₉₀ is better than the placebo by the CSD is less than 0.05 (with ≤ 300 subjects randomized) or 0.075 (with ≥ 350 subjects randomized) at 12 months of treatment. If the study meets statistical futility criteria, the sponsor will make the final decision pertaining to study futility after reviewing recommendations by the DSMB. Based on Sponsor's final decision, if the study continues to randomize subjects, it will be considered a failed study.

Study Success: The study will be considered a success if either of the following criteria are met for the 12 month treatment endpoint:

1. The study meets early success criteria (as outlined above)
2. The study reaches complete randomization and the Bayesian analysis at completion of 12 months of treatment results in an ED₉₀ with at least an 80% probability of being better than the placebo by the CSD

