Item	Algorithm	Handling Missing Data	Score Range
1. Word Recall	Total the number of “No” responses for each trial. The subscore is the sum the scores from trials 1, 2, and 3, divide by 3.	If a trial is missing or partially done then trial score is missing. If a trial score is missing then the subscore is missing	0 to 10
2. Commands	Total the number of “No” responses from the 5 tasks	If any task is missing then the subscore is missing	0 to 5
3. Constructional Praxis	Count the number of “No” responses. The subscore is 0 = all 4 drawings correct 1 = 1 figure drawn incorrectly 2 = 2 figures drawn incorrectly 3 = 3 figures drawn incorrectly 4 = 4 figures drawn incorrectly 5 = no figures drawn, scribbles, parts of forms	If any task is missing then the subscore is missing	0 to 5
4. Delayed Word-Recall	Total the number of “No” responses.	If any response is missing then subscore is missing	0 to 10
5. Naming Objects / Fingers	Total the number of “No” responses. The subscore is 0 = 0-2 “no” responses 1 = 3-5 “no” responses 2 = 6-8 “no” responses 3 = 9-11 “no” responses 4 = 12-14 “no” responses 5 = 15-17 “no” responses	If any response is missing then subscore is missing	0 to 5
6. Ideational Praxis	Total the number of “No” responses.	If any response is missing then subscore is missing	0 to 5
7. Orientation	Total the number of “No” responses.	If any response is missing then subscore is missing	0 to 8
8. Word Recognition	For each trial, total the number of “1” responses. If the total is 12 or less, then the trial score = total. If the total is > 12 then trial score=12. The subscore is the sum the scores from trials 1, 2, and 3, divide by 3.	If a trial is missing or partially done then trial score is missing. If a trial score is missing then the subscore is missing	0 to 12
9. Remembering Test Instructions	The subscore is 0 = None, 1 = Very Mild, 2 = Mild, 3 = Moderate, 4 = Moderately Severe, 5 = Severe	If the response is missing then subscore is missing	0 to 5

10. Comprehension	The subscore is 0= None, 1= Very Mild, 2= Mild, 3= Moderate, 4= Moderately Severe, 5= Severe	If the response is missing then subscore is missing	0 to 5																					
11. Word Finding Difficulty	The subscore is 0= None, 1= Very Mild, 2= Mild, 3= Moderate, 4= Moderately Severe, 5= Severe	If the response is missing then subscore is missing	0 to 5																					

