5.5 Superior to Control

At the conclusion of the study, the d_{ED90} will be considered superior to control if the posterior probability the d_{ED90} has greater mean change at 52-weeks is at least 97.5%.

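### Appendix 13.2 counts a larger change in the composite score as benefit without declaring a sign reversal, so its decision formulas contradict ADCOMS and the CSD as the main text defines them

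*SAP*

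**What the plan says.** **The endpoint.** SAP Section 5.4.1 adds the ADAS-Cog and CDR items with positive weights and reverses the two MMSE items: "A11 * 0.016211 + (5-M1) * 0.041567 + (1-M7) * 0.038238 + C1 * 0.054321". It adds: "The range of this new composite score is therefore between 0 and 1.97". In Section 8.2 the ADAS-Cog items count failures or rate severity. The rated items, word finding among them, run "0 = None, 1 = Very Mild, 2 = Mild, 3 = Moderate, 4 = Moderately Severe, 5 = Severe". The MMSE counts correct answers.

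**The rules in words.** Section 5.4.2 describes the CSD as an "approximate 25% reduction compared to placebo in the progression of AD as measured by the derived ADCOMS". Sections 5.4.1, 5.4.2, 6.1 and 6.2 state success and futility through the probability that the ED90 dose beats placebo by, or achieves, the CSD. They give no formula and no numerical CSD. Section 5.4.2 refers to Appendix 13.2 for details.

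**The rules as formulas (Appendix 13.2).** Section 1.0 sets the CSD at 0.03. Section 2.1 models the change from baseline to 52 weeks in a composite clinical score. Section 2.2 defines θ_d: "We label the mean change from baseline to 52-weeks for dose group" d. The criteria are then:
- Section 3.2, superiority: Pr(θ_d > θ_0).
- Section 3.3, superiority by the CSD: "The proportion of pairs where the treatment effect for the active dose is greater than for control by at least 0.03", that is Pr(θ_d > θ_0 + 0.03).
- Section 3.4, phase III success: Pr(θ_0 > θ_d) < 0.025.
- Section 5.1, futility: the CSD probability for the ED90 is below 0.05, or below 0.075 from the 350-patient look.
- Sections 5.2 and 5.3, success: the same probability exceeds 0.95 at an interim look, or 0.80 at completion.
- Section 5.5, final superiority: the posterior probability that the ED90 "has greater mean change at 52-weeks is at least 97.5" percent.

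Section 5.4.4 carries the same model to 18 months and takes from it the ED90 used in the ED90-versus-placebo comparisons.

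**The concern.** If ADCOMS rises with worsening, benefit is a smaller change than on placebo, so θ_d should lie below θ_0. Every formal criterion in the appendix asks for θ_d above θ_0. No sentence says that the score was multiplied by minus one or that a positive change means improvement.

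The numerical margin and the inequalities appear only in the appendix, so anyone programming or checking the rules must use it. A literal reading credits the dose whose patients decline more. Nor can a reader verify from the document which direction was used.

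**Working it through.** **1. Direction of ADCOMS.** Section 5.4.1 weights, with item maxima from Section 8.2:
- ADAS-Cog: 10×0.00847483 + 8×0.017088 + 12×0.003732761 + 5×0.016211 = 0.3473
- MMSE, both items failed: 5×0.041567 + 1×0.038238 = 0.2461
- CDR: 3×(0.054321 + 0.1091 + 0.089039 + 0.069493 + 0.058724 + 0.078152) = 1.3765

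The total at full impairment is 1.970, matching the stated 1.97, and it is 0 at no impairment. Higher is worse.

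**2. Reproducing the plan's own figure.** Table 7.6.B gives 0.923 for 10BM, with model estimates 0.067 against 0.012 (difference 0.055). Normal approximation: Pr = Φ((difference − 0.03)/SE), with SE = 0.15·√(1/n0 + 1/n1).
- All randomised (185, 160): SE 0.0162, Φ(0.025/0.0162) = 0.939.
- Week-52 completers (114, 93): SE 0.0210, Φ(0.025/0.0210) = 0.884.
- A Gibbs sampler for the two-dimensional NDLM, with σ fixed at 0.15 and the Table 7.6.A week-52 means, gives 0.917 with all randomised and 0.848 with completers.

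The stated 0.923 falls in this range. The example was therefore computed with a larger positive change counted as benefit.

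**3. The formula applied literally to ADCOMS change.** Take a true-scale difference of 0.06 in either direction. The third row uses the SE implied by Table 7.5.B, the interim look with 185 and 160 randomised but only 38 and 19 with week-52 data. There the model estimates are 0.074 and 0.006 and the stated probability is 0.957, so SE = (0.068 − 0.03)/1.717 = 0.0221.

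| Basis for SE | SE | Drug worsens by 0.06: Φ(0.03/SE) | Drug slows by 0.06: Φ(−0.09/SE) |
|---|---|---|---|
| 185 v 160, all with week-52 data | 0.0162 | 0.968 | 0.00000001 |
| 114 v 93 completers | 0.0210 | 0.924 | 0.00001 |
| Implied by Table 7.5.B | 0.0221 | 0.91 | 0.00002 |

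Under the reversed inequality, Pr(θ_0 − θ_d > 0.03), the last two columns change places.

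**4. Which dose is tested.** The rules apply to the identified ED90. With the example's week-52 means sign-flipped in the same NDLM, the written formula gives 0.000 for 10BM, but its highest value over the doses is 0.098 (all randomised) or 0.126 (completers). Both exceed the 0.075 futility boundary.

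**5. Effect on the simulations.** The priors for θ_0 and θ_1 and for the longitudinal intercepts are centred at 0. The other doses follow a random walk, and the regression slope is unchanged when both scores change sign. The model is therefore the same for Y and −Y.

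**The case against.** The strongest reply is that the appendix shows its convention even though it does not state it. The worked example calls the 10Q result at 12 weeks worse where Table 7.1.A shows −0.02. Later it describes positive values as a positive or strong effect. Table 8.2 lists positive values as treatment effects, and Sections 3.2 and 3.3 call draws of θ_d treatment effects. The appendix never names ADCOMS. Read as a whole it is coherent with positive meaning improvement. This stands, and it makes an undeclared sign reversal the likely cause. It does not remove the conflict with Sections 2.1 and 2.2 of the same appendix or with SAP Sections 5.4.1 and 5.4.2.

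A second reply is also right. The main-body rules have the correct direction, so it would be wrong to say that the SAP's success and futility rules as a whole are written backwards.

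A third reply concerns timing. SAP v4.0 is dated 05 Jun 2018 and the listed interim reports run to 05 Dec 2017, so an edit cannot alter those decisions. What remains is the 18-month Bayesian analysis, which is a sensitivity analysis, and the record of what was coded. Section 10 says that a validated algorithm is used for the NDLM, but it does not state the direction.

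**Conclusion.** The point holds as a contradiction within the document. The appendix's formulas, applied to the endpoint as the SAP defines it, give the opposite decision to the main-body rules. For a 0.06 worsening the written probability is about 0.91 to 0.97, depending on week-52 completeness. For a 0.06 slowing it is near 0. These figures assume SD 0.15, the example trial's sample sizes and a normal approximation.

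A reader might infer more, but the documents do not support it:
- *That the trial was run in the wrong direction, or that its type I error and power are wrong.* Nothing shows wrong code, and the model is symmetric under a change of sign, so the operating characteristics need not change.
- *That a harmful dose would be declared an early success.* The 0.968 treats every randomised subject as having week-52 data. The plan's own interim table implies about 0.91, and completers give 0.924. The 0.80 completion rule is met, but not necessarily the 0.95 rule.
- *That any drug that slows decline would stop for futility.* This follows when the slowing dose is the identified ED90. If another dose has little effect, the literal ED90 may be that dose, and its probability can stay above 0.075.
- *That the decision rules drive dose ranking and randomisation.* The order is the reverse. d_Max and ED90 are derived first (Appendix Section 3.1, where the greatest difference from control carries no stated sign). They then enter the rules and the allocation weights.

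**What to change.** Choose one convention and state it once. Either:
- in Appendix 13.2 Section 2.1, define Y as minus the change from baseline in ADCOMS, so that positive means improvement and the existing inequalities stand; or
- keep Y as the ADCOMS change and rewrite the criteria as Pr(θ_d < θ_0) and Pr(θ_0 − θ_d > 0.03) in Sections 3.2 to 3.4, 5.1 to 5.3 and 5.5, with d_Max and ED90 in Section 3.1 based on the largest reduction relative to control.

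The first option is the smaller edit and leaves the worked example and scenario tables as they are. State in SAP Section 5.4.4 that the 18-month Bayesian analysis uses the same convention. Ask the independent data analysis group to confirm in writing the direction coded. The cost is a wording change and one code check, with no new data. Given step 5, the operating characteristics need not be re-simulated if the check confirms the direction.

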3.4 Probability of Phase III Success

For each active dose, we calculate the predictive probability of success in a phase III trial. We assume a hypothetical future phase III trial with a fixed design that would equally randomize 500 patients between control and an active dose (250 per arm). The predictive probability of phase III success is the chance of statistical significance ($\Pr(\theta_0 > \theta_d) < 0.025$) versus control if the active dose was entered into the hypothetical future phase III trial.

This is different from the power for such a trial, in that power calculations typically assume a fixed treatment effect whereas the predictive probability of success averages the power over the posterior distribution of the treatment effect. Thus knowledge of the treatment effect and the uncertainty in that knowledge are formally incorporated.

We determine the predictive probability of phase III success for a dose, d , by randomly sampling one value from the posterior distribution of the treatment effect for that dose and a corresponding random sample from the posterior distribution of the treatment effect for control. Assuming these treatment effects, we calculate the corresponding power (i.e., the probability of phase III success or the probability that $\Pr(\theta_0 > \theta_d) < 0.025$ given the randomly sampled treatment effects) and record that result. We repeat this 10,000 times. The average of the resulting probabilities of phase III success is the predictive probability of phase III success.

